## **SUMMARY OF CHANGES FOR AMENDMENT 1**

Protocol Section Change				
Cover Page	Study Principal Investigators, Site, and Institutional Review Board changed to reflect change in study site to			
1.3 Study Setting; 3.1 Study Setting; elsewhere, as needed	Study site changed to PPD			
2.3 Hypotheses	Added clarifying statement that no formal hypotheses will be tested.			
Figure 3-1: Vaccinated Cohorts	Clarified that for Regimen Initiators and Autoimmune Cohorts, males must be health plan members at time of vaccination with GARDASIL TM .			
3.4.1 General Safety Cohorts: Regimen Initiators and Regimen Completers	Clarified continuous enrollment membership criterion for Regimen Completers cohort. Removed statement regarding the analyses to be conducted on each cohort (replaced with more comprehensive table added to Section 4.1.2).			
3.4.3 General Safety and Autoimmune Cohort Exclusion Criteria	For Regimen Completers cohort, deleted post-vaccination self-comparison membership exclusion criterion. Males will be censored when membership expires.			
3.5 Accrual of Study Subjects and Accrual Timelines	Removed study vaccine provisioning language as it is no longer relevant for this study setting.			
3.6.1 General Safety Endpoints and Risk Periods	Clarified that all health outcomes resulting in emergency room visit or hospitalization will be evaluated in this study, including venous embolism and thrombosis.			
3.6.1 General Safety Endpoints and Risk Periods	Clarified how health outcomes will be identified within the PPD database.			
3.6.1 General Safety Endpoints and Risk Periods	Clarified that for sub-analyses in which pre-existing chronic conditions are excluded, decision rules and methods will be described in the study's Data Analysis Plan.			
3.6.1 General Safety Endpoints and Risk Periods	For clarity, removed sentence regarding self-comparison periods. Self-comparison periods are described in detail in Section 3.7.1			
3.6.1 General Safety Endpoints and Risk Periods	Clarified rationale for limiting Day 0 events to prespecified outcomes of interest.			

## SUMMARY OF CHANGES FOR AMENDMENT 1 (CONT.)

Protocol Section	Change			
3.6.2 Identification of Pre-	To be consistent with one-year membership criterion for			
specified, New-Onset	Autoimmune Cohort, exclusion of pre-existing conditions			
Autoimmune Endpoints	identified from codes in the PPD database will			
	be limited to one year (rather than two years) prior to a			
	subject's first dose of GARDASIL TM .			
3.6.2 Identification of Pre-	To allow for a thorough review of pre-existing symptoms			
specified, New-Onset	and diagnoses, medical records (when available) of			
Autoimmune Endpoints	potential cases in the Autoimmune Cohort will be			
	reviewed from at least 2 years (rather than 1 year) prior to			
	a subject's first dose of GARDASIL TM .			
3.6.2 Identification of Pre-	Clarified that Case Review SOP will specify procedures			
specified, New-Onset	for reconciling disagreements between the case reviewers			
Autoimmune Endpoints	with respect to the diagnosis or date of symptom onset.			
	Removed statement that procedure will be majority rule;			
	consensus or other approach may be preferable. (Final			
	approach will be agreed upon by Case Review			
	Committees and Safety Review Committee.)			
3.7.1 General Safety	Added statement clarifying the value of using self-			
Comparison Population	comparison approach.			
3.7.1 General Safety	For analyses using Day 1-60 risk periods, post-			
Comparison Population	vaccination self-comparison person-time accrual will			
and Figure 3-2 Footnote	begin after a 60-day risk period and 30-day washout			
	period after any dose (not limited only to last dose).			
3.7.1 General Safety	Clarified that post-vaccination self-comparison periods for			
Comparison Population	Day 0 and Day 1-14 analyses will require a health care			
	visit day as much as possible, and that self-comparison			
	period for Day 1-14 analyses will be 14 days in length.			
3.7.2 Autoimmune	Added potential use of propensity score matching for			
Comparison Population	autoimmune background cohort comparison (to help limit			
2.7.2.4	confounding).			
3.7.2 Autoimmune	Deleted use of post-vaccination self-comparison for			
Comparison Population;	Autoimmune Cohort, after further evaluation of logistical			
4.2 Autoimmune Study	feasibility. Deleted Figure 3-3 (Autoimmune Self-			
Population Analysis	Comparison figure). Added statement to Section 4.2 that			
	autoimmune post-vaccination self-comparison approach			
	could be one of many options the Safety Review			
	Committee can recommend if further evaluation of			
	autoimmune conditions is needed after background rate			
	comparison is undertaken.			

Protocol/Amendment No.: 070-01

## SUMMARY OF CHANGES FOR AMENDMENT 1 (CONT.)

Protocol Section	Change				
4.1.2 Relative Risks	Added Table 4-1 to summarize the analyses to be				
	conducted in the study. Added separate analysis of each				
	dose for Regimen Completer cohort, to assist in				
	evaluating dose-specific safety. Removed redundant				
	analyses from Regimen Completer cohort that are already				
	planned for Regimen Initiator cohort (completers are a				
	subset of initiators).				
Global	"Incidence rates" replaced with "incidence" to reflect the				
	possibility that for some analyses with limited person-				
	time, risk ratios (based on number of events per number of				
	subjects) may be used rather than rate ratios.				
Global	Minor editorial revisions for clarification purposes.				

#### LIST OF ABBREVIATIONS

ACIP Advisory Committee on Immunization Practices

ADEM Acute disseminated encephalomyelitis

AHA Autoimmune hemolytic anemia

AS Ankylosing spondylitis CDC Centers for Disease Control

CI Confidence interval

CIOMS V Council for International Organization of Medical Sciences

CPT Current Procedural Terminology

CRC Case Review Committee
EMEA European Medicines Agency
FDA Food and Drug Administration
GBS Guillain-Barre syndrome
HCFA Healthcare Financing Agency

HCPCS Healthcare Common Procedure Coding System
HIPAA Health Insurance Portability & Accountability Act

HPV Human papillomavirus

HCUP Healthcare Cost and Utilization Project

IEC Independent Ethics Committee
IRB Institutional review board
ITP Immune thrombocytopenia
JRA Juvenile rheumatoid arthritis

MS Multiple sclerosis
NDC National Drug Code
RA Rheumatoid arthritis

RR Relative risk

SAE Serious Adverse Event

SLE Systemic lupus erythematosus SOP Standard operating procedures SRC Safety Review Committee

US United States

7

Protocol/Amendment No.: 070-01

#### **SYNOPSIS**

Background and Rationale: GARDASILTM is Merck's (the SPONSOR's) quadrivalent human papillomavirus (HPV) vaccine. The vaccine was approved in 2006 by the United States (US) Food and Drug Administration (FDA) and European Medicines Agency (EMA) for the prevention of several diseases caused by HPV types 6, 11, 16, and 18 in females. In October 2009, the US FDA approved GARDASILTM for use in boys and men, 9 through 26 years of age, for the prevention of external genital warts (condyloma acuminata) caused by HPV types 6 and 11. In December 2010, the US FDA approved GARDASILTM for use in males and females, 9 through 26 years of age, for the prevention of anal intraepithelial neoplasia (AIN) grades 1, 2, and 3 caused by HPV types 6, 11, 16, and 18, and for the prevention of anal cancer caused by HPV types 16 and 18. This observational study of the safety of GARDASIL in males is a post-licensure regulatory commitment after the October 2009 approval of GARDASILTM in males.

Study Setting: The study will be conducted in collaboration with PPD The study population will be drawn from a proprietary research database containing eligibility, pharmacy claims, and medical claims data from a large US health plan affiliated with PPD The study protocol will be submitted to an Institutional Review Board (IRB) for review and approval. The SPONSOR will not have access to any individual patient's medical information. The data will be analyzed by the study investigators and only aggregated data with no personal identifiers will be provided to the SPONSOR.

**Objectives:** The primary objective of this study is to describe the general safety of GARDASILTM among males within 60 days following the administration of each dose of the vaccine by estimating: a) the incidence of health outcomes resulting in emergency room visits or hospitalizations occurring in combined 60-day risk periods after each dose of GARDASILTM; and b) the relative risk of such health outcomes as compared to incidence in a post-vaccination self-comparison reference period.

The three secondary objectives are:

- 1) To describe the general safety of a  $\underline{first\ dose}$  of GARDASIL  $^{TM}$  in males;
- 2) To provide descriptive epidemiology of 20 pre-specified new-onset conditions (collectively termed "autoimmune conditions" for the purposes of this protocol) for a period of 6 months after each dose of GARDASILTM, including comparison of incidence of these conditions to background incidence within the male population of similar age distribution; and
- 3 ) To describe the general safety of  $\mathsf{GARDASIL}^\mathsf{TM}$  on the day of vaccination in males.

**Hypotheses:** This is a descriptive observational study designed to provide data on the safety of GARDASILTM in young males in the course of routine clinical practice. No formal hypotheses will be tested.

Committees: Study results will be provided for review and interpretation to the Safety Review Committee (SRC), an independent committee of experts, external to and the SPONSOR, in charge of monitoring the safety data emerging from the study. In addition, several Case Review Committees (CRCs) will be comprised of independent, expert physicians, whose role will be to review redacted medical records to confirm potential diagnoses of the pre-specified autoimmune conditions of interest identified from the PPD database.

**Study Subjects and Accrual:** There will be no active enrollment of study subjects. Study subjects will receive GARDASILTM as part of their routine medical care. Recipients of GARDASILTM will be identified in PPD database. General safety will be monitored in two cohorts:

- 1) Regimen Initiators (any male health plan member with at least one dose of GARDASIL);
- 2) Regimen Completers (any male health plan member between the ages of 9 and 26 years at first dose, who completed the 3-dose vaccination regimen within a pre-specified period of time).

Pre-specified autoimmune conditions will be monitored within the Autoimmune Cohort, which is a subset of the Regimen Initiators cohort with at least one year of health plan membership prior to their first dose (to help identify pre-existing conditions).

Accrual of study participants will continue until the earliest of:

- 1) accrual of 135,000 males in the general safety Regimen Initiators cohort;
- 2) accrual of 44,000 males in the general safety Regimen Completers cohort; or
- 3) six years after study start date. Interim annual and final reports are planned.

**Study Endpoints:** The general safety endpoints are all health outcomes resulting in an emergency room visit or hospitalization in each of the following time periods immediately after vaccination (referred to as "risk periods") as follows: Days 1-60, Days 1-14, and Day 0 (for the conditions identified in secondary objective 3). These health outcomes will be grouped into pre-defined categories, using the Healthcare Cost and Utilization Project (HCUP) coding structure. HCUP is a comprehensive and well-established grouping structure that offers a pre-specified hierarchical grouping of all ICD-9 diagnosis codes into a manageable number of clinically meaningful categories.

Protocol/Amendment No.: 070-01

For the autoimmune analysis (secondary objective 2), all pre-specified new onset conditions occurring within 180 days after any dose, as identified from outpatient, emergency room visits, or hospitalizations, will be evaluated.

**Comparison Groups**: For the analysis of general safety, the recipients of GARDASILTM will serve as their own "controls" for any health outcome identified from emergency room visits and hospitalizations. For each general safety health outcome, the incidence rate of the health outcome observed during a post-vaccination self-comparison period will serve as a background rate to which the incidence rate observed in the risk periods immediately following vaccination will be compared. For the Day 1-14 and Day 0 risk period analyses, the post-vaccination self-comparison period will include a health care visit during that period to the extent possible.

For the autoimmune analysis, the comparison group will be an age-matched population of males from the health plan, not vaccinated with GARDASIL TM within the time period during which the autoimmune cases were vaccinated.

**Data Analysis:** For the general safety and autoimmune cohorts, descriptive statistics will be summarized in the study reports. When either the Regimen Initiator or Regimen Completer cohort accrues at least 22,000 males, incidence and relative risks will also be calculated. A multiplicity adjustment will be applied to take into account the large number of comparisons being made. However, all results (adjusted and unadjusted) will be included in study reports.

For the autoimmune analysis, incidence and relative risks will also be calculated. Propensity score matching is expected to be used for the background autoimmune comparison cohort.

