#### 2.2 SECONDARY OBJECTIVES

The three secondary objectives of this study are:

- 1. To describe the general safety of a first dose of GARDASILTM in males by estimating: a) the incidence of health outcomes resulting in emergency room visits or hospitalizations in the 60-day risk period following the first dose of GARDASILTM; and b) the relative risk of such health outcomes as compared to incidence rates in a post-vaccination self-comparison reference period.
- 2. To provide descriptive epidemiology of the following pre-specified new-onset conditions for a period of 6 months after each dose of GARDASILTM, including comparison of incidence of these new-onset conditions, identified from the outpatient, emergency room, and hospital setting, to background incidence within the PPD male population of similar age distribution. These pre-specified conditions are considered conditions of interest, although no safety signals have been found in the GARDASILTM trials or in postmarketing surveillance. For ease and clarity of reference, these conditions will collectively be referred to as "autoimmune conditions" hereafter in this protocol, though it is acknowledged that they are actually a broader group of conditions.
  - Rheumatologic/autoimmune disorders: immune thrombocytopenia (ITP), autoimmune hemolytic anemia (AHA), systemic lupus erythematosus (SLE), rheumatoid arthritis (RA), juvenile rheumatoid arthritis (JRA), psoriatic arthritis, ankylosing spondylitis (AS), reactive arthritis, Crohn's disease, and ulcerative colitis;
  - Autoimmune endocrine conditions: type 1 diabetes, Hashimoto's disease, Graves' disease;
  - Autoimmune neurologic and ophthalmic conditions: multiple sclerosis (MS), acute disseminated encephalomyelitis (ADEM), other demyelinating diseases of the nervous system, Guillain-Barré syndrome (GBS), neuromyelitis optica, optic neuritis, and uveitis.

Protocol/Amendment No.: 070-01

3. To describe the general safety of GARDASILTM on the day of vaccination (i.e., Day 0) among young males by estimating the incidence of the following health outcomes on the day of vaccination, and estimating relative risk of these health outcomes as compared to incidence rates in a post-vaccination self-comparison period:

- Syncope, convulsive syncope;
- Epilepsy, convulsions;
- Head trauma;
- Allergic reactions.

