## 3.4.1 General Safety Cohorts: Regimen Initiators and Regimen Completers

For monitoring general safety, there will be two cohorts:

- 1) **Regimen Initiators:** Males who received at least one GARDASILTM vaccination administered after FDA licensure for males (October 2009). Males in this cohort will be required to be members of the health plan affiliated with "(hereafter referred to as "the health plan") at the time of GARDASILTM receipt.
- 2) Regimen Completers: Male health plan members who received exactly 3 doses of GARDASILTM after FDA licensure for males (October 2009). This cohort will be limited to subjects who received GARDASILTM per protocol (male, 9-26 years of age at time of the first dose, the first and third dose administered within 12 months with intervals of at least 28 days between dose 1 and dose 2, 12 weeks between dose 2 and dose 3, and 24 weeks between dose 1 and dose 3). With the exception of the allowance of a 12-month interval between the first and third doses, this is the administration regimen recommended by the CDC Advisory Committee on Immunization Practices (ACIP) [4]. ACIP specifies a 6-month interval for regimen completion. A 12-month interval was selected for this study to provide sufficient flexibility for accrual within the Regimen Completers cohort, as not all 3-dose completers will adhere exactly to a 6-month completion regimen. Males in this cohort will be required to be continuously enrolled into the health plan (with allowance for standard grace periods that account for brief lapses in membership) through the receipt of all three GARDASILTM doses.

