#### 3.4.2 Autoimmune Cohort

For evaluation of pre-specified, new-onset autoimmune conditions, the cohort will be the same as the general safety cohort of Regimen Initiators (at least one dose of GARDASILTM), except that the cohort will include only males who were members of the health plan during the 12-month period prior to their first dose of GARDASILTM. This membership criterion will assist in determining whether a condition is new-onset after receipt of GARDASILTM or considered as pre-existing. A description of the autoimmune comparison population of male in the health plan who were not vaccinated with GARDASILTM is provided in Section 3.7.2.

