#### 3.4.3 General Safety and Autoimmune Cohort Exclusion Criteria

As a general rule, all males vaccinated with at least one dose of GARDASILTM after the approval of the male indication in the US will be included in the study.

For the general safety cohorts, the following exclusion criteria will apply:

- any females;
- males vaccinated prior to the FDA date of licensure of GARDASILTM for males for the prevention of external genital warts (October 2009); and/or
- males who received all doses of GARDASILTM outside of the health plan.

Specific to the Regimen Completers cohort, the following additional exclusion criteria will also apply:

- any male outside the 9-26 year old age range at first dose;
- males who were not health plan members at each GARDASILTM dose;
- males who completed the 3-dose regimen of GARDASILTM over a period greater than 12 months;
- males who had less than a 28-day interval between the first and second dose;
- males who had less than 12 weeks between the second and third dose; and/or
- males who had less than 24 weeks between the first and third dose.

For the autoimmune cohort of males vaccinated with GARDASILTM, the following exclusion criteria will apply (i.e., same as for general safety plus requirement of 12 months of health plan membership prior to vaccination):

- any females;
- males vaccinated prior to the FDA date of licensure of GARDASILTM for males for the prevention of external genital warts (October 2009);
- males who received all doses of GARDASILTM outside of the health plan; and/or
- males with less than 12 months of health plan membership prior to their first dose of GARDASILTM.

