#### 3.5 ACCRUAL OF STUDY SUBJECTS AND ACCRUAL TIMELINES

As specified by the FDA, accrual of study participants will continue until the earliest of:

- 1) accrual of 135,000 males in the general safety Regimen Initiators cohort;
- 2) accrual of 44,000 males in the general safety Regimen Completers cohort; or
- 3) six years after study start date (as further described in Section 3.9).

There will be no active enrollment of study subjects. Study subjects will receive  $GARDASIL^{TM}$  as part of their routine medical care.

Recipients of GARDASILTM will be identified in PPD database. Vaccination details, such as date of vaccination, are available in the electronic claims records.

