## General Safety Cohorts: Example of Risk Periods and Post-Vaccination Self-Comparison Periods

(Length and timing of actual periods will vary according to number of doses received and vaccination schedule of each study subject)

\*Post-vaccination self-comparison person-time will begin 91 days after each dose, thus allowing a 60-day risk window and 30-day "washout" period after each dose. In this example, the post-vaccination self-comparison time is the combined time of month 5-6 and 9-14.

ICD-9 diagnosis codes listed in any position (primary or secondary) in the database for an emergency room visit or a hospitalization occurring during the risk (or self-comparison) periods will be included in the general safety analysis, irrespective of whether it is a new diagnosis code for the patient or corresponds to a pre-existing condition or a prior episode of the health outcome. In addition, to provide interpretation context for the SRC for the primary general safety objective, the analysis will be re-run excluding chronic pre-existing conditions. The methods and decision rules for identifying and excluding chronic pre-existing conditions will be described in the study's Data Analysis Plan. The subject would still be included in analyses of all other health outcomes for which he does not have a pre-existing condition.

To facilitate the analysis and interpretation of results, all ICD-9 diagnosis codes listed for emergency room visits and hospitalizations occurring during the risk or self-comparison periods will be grouped into pre-defined health outcome categories, using the Healthcare Cost and Utilization Project (HCUP) coding structure [5]. HCUP is a comprehensive and well-established grouping structure that offers a pre-specified hierarchical grouping of all

ICD-9 diagnosis codes into a manageable number of clinically meaningful categories. The specific HCUP categories and subcategories of interest for this study will be prespecified before any analysis is performed, with concurrence from the SRC.

For events occurring on the date of vaccination (Day 0), emergency room visits and hospitalization health outcomes of interest will be limited to pre-specified, syncope, convulsive syncope; epilepsy, convulsions; head trauma; and allergic reactions. These Day 0 health outcomes of interest were pre-specified based on consideration of temporal and biological plausibility for an association with an injection or vaccination.

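### The Regimen Initiator 'Dose 1' analysis can count a second or third dose as the first, because no membership before the first recorded dose is required

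*Protocol*

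**What the plan says.** All references are to the protocol.

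- **Entry.** The synopsis defines "Regimen Initiators (any male health plan member with at least one dose of GARDASIL". The operative rule in Section 3.4.1 reads "Males in this cohort will be required to be members of the health plan affiliated with" the study's research partner, at the time the vaccine is received. No minimum period of earlier membership is set.
- **Doses elsewhere.** Section 3.4.3 excludes "males who received all doses of GARDASIL TM outside of the health plan". A male with some doses outside and at least one inside stays in. The same section separately excludes Regimen Completers who were not members at each dose; Initiators have no such line.
- **How doses are seen.** Section 3.5: "Vaccination details, such as date of vaccination, are available in the electronic claims records".
- **First-dose objective.** Secondary Objective 1 (Section 2.2) estimates "the incidence of health outcomes resulting in emergency room visits or hospitalizations in the 60-day risk period following the first dose of" the vaccine. Table 4-1 runs a Dose 1 row in Regimen Initiators for Days 1-60, Days 1-14 and Day 0.
- **Contrast.** For the Autoimmune Cohort, Section 3.4.2 states that "the cohort will include only males who were members of the health plan during the 12-month period prior to their first dose of" the vaccine.

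**The concern.** The Dose 1 row is meant to isolate the first exposure. Dose number is read from plan claims, and nothing in the cohort criteria establishes that the first dose on record is the first dose received. A male vaccinated once under another insurer, who joins the plan and then has his second dose, satisfies every Initiator criterion and appears with dose 2 as his first.

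If the vaccine had an effect specific to the first exposure, mixing in later doses would pull the estimate toward 1. If the effect belonged to later doses, part of it would surface under the Dose 1 label. The first direction is the more awkward one in a safety commitment, because it makes a signal easier to miss.

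The all-doses-combined analysis that serves the primary objective does not depend on dose number, so the point is confined to the Dose 1 analyses.

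**Working it through.** **1. The plan's own figure.** The nearest stated numbers are in Section 4.1.5: 50% power for a relative risk (RR) of 2 and 92% for an RR of 3, with 132,000 doses, background 1 per 12,000 doses and two-sided alpha 0.05. With equal risk and comparison windows, expected events are E0 = 132,000/12,000 = 11 in the comparison time and E1 = 11 × RR in the risk time. For rare events, power ≈ Φ[(E1 − E0)/√(E0 + E1) − 1.96].

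- RR 2: (22 − 11)/√33 = 1.915; 1.915 − 1.96 = −0.045; power 48.2%.
- RR 3: (33 − 11)/√44 = 3.317; 3.317 − 1.96 = 1.357; power 91.3%.

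Both are within 2 points of the stated values, so the formula can be used for illustration. The concern itself does not depend on it.

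**2. Can a later dose be counted as Dose 1?**

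| Rule | Where | Does it stop a male whose dose 1 was under other coverage? |
|---|---|---|
| Member when the vaccine is received | 3.4.1 | No. He is a member at his first recorded dose, and an earlier dose outside the plan cannot be checked. |
| All doses outside the plan | 3.4.3 | No. He has at least one inside. |
| Vaccinated before licensure for males | 3.4.3 | No. This concerns date, not dose number. |
| Doses taken from claims | 3.5 | No. A dose paid by another insurer would not ordinarily appear. |
| 12 months' prior membership | 3.4.2 | Would help, but applies only to the Autoimmune Cohort. |

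No rule stated in the protocol prevents it.

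**3. Size of the dilution.** Let f be the share of recorded first doses that are really dose 2 or 3. The documents do not give f; 1% to 20% is an assumed range. With the same background incidence in both groups, observed RR = (1 − f) × RR(dose 1) + f × RR(later). If later doses carry no excess, RR(later) = 1 and observed RR = 1 + (1 − f)(RR − 1). Power is shown for an illustrative 132,000 first doses and background 1/12,000.

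| f | True RR 3: observed | Power | True RR 2: observed | Power |
|---|---|---|---|---|
| 0 | 3.00 | 91.3% | 2.00 | 48.2% |
| 1% | 2.98 | 90.9% | 1.99 | 47.6% |
| 5% | 2.90 | 89.1% | 1.95 | 45.0% |
| 10% | 2.80 | 86.5% | 1.90 | 41.8% |
| 20% | 2.60 | 79.9% | 1.80 | 35.4% |

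**4. The opposite case.** If dose 1 carries no excess and later doses have RR 3, the Dose 1 row would show (1 − f) + 3f = 1 + 2f: 1.02, 1.10, 1.20 and 1.40 at the same four shares.

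**The case against.** The strongest reply is that Table 4-1 already contains a cleaner Dose 1 analysis. Regimen Completers have exactly three recorded doses at specified minimum intervals and continuous enrolment through all three. A male whose dose 1 was given elsewhere would rarely have three plan doses of a three-dose series, so that row is largely free of mislabelling. This stands, but only as a partial check: the row appears in the final report only, has no Day 0 analysis, and omits males who stopped after dose 1, who may include those who reacted to it.

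It can also be said that the frequency is unknown, that the effect is small if mislabelling is rare, and that the study is descriptive with no formal hypotheses. All of that is true and limits the weight of the point. It does not remove it, since estimating first-dose risk is a stated objective.

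Three stronger readings are tempting, and the documents do not support them.

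- *The protocol deliberately admits males at dose 2 or 3.* The Section 3.4.3 wording equally keeps males with dose 1 in the plan and later doses elsewhere, who cause no mislabelling. Entry at a later dose is permitted; it is not stated to occur.
- *The re-run in which "the analysis will be re-run excluding chronic pre-existing conditions" has no history to screen.* Section 3.6.1 leaves its methods and decision rules to the Data Analysis Plan, which is not at hand and may set a look-back. The synopsis also makes the Autoimmune Cohort a subset of Initiators with at least a year of prior membership, so those males do have history.
- *The restricted cohort must replace the full one for Dose 1.* Section 3.4.3 sets a general rule of including all males vaccinated with at least one dose after the male approval, and dropping recent joiners from the main analysis is a debatable trade.

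**Conclusion.** The point holds for the Initiator Dose 1 analyses, and only there. As the cohort is defined, a second or third dose can be counted as a first dose, and no rule in the protocol establishes dose number.

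The size cannot be fixed from the documents. Assuming no excess risk after later doses and equal background incidence, an RR of 3 falls to 2.98 at 1% mislabelling and 2.6 at 20%; in the illustration, power falls from 91.3% to 90.9% and 79.9%. This is a cheap improvement to Secondary Objective 1. It is not a flaw that invalidates that objective, and the primary all-doses analysis is untouched.

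**What to change.** Keep the all-Initiator Dose 1 analysis as it is. Add to Table 4-1, with a matching sentence in Section 3.4.1, a pre-specified Dose 1 analysis for Days 1-60, Days 1-14 and Day 0 in Initiators who have at least 12 months' membership before the first recorded dose and no GARDASIL claim before that dose. Report the two results side by side, in the interim reports that carry relative risks and in the final report. Agreement would suggest that mislabelling matters little; a clear difference would tell the Safety Review Committee to read the full-cohort Dose 1 result with care, bearing in mind that recent joiners may differ in other ways.

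The membership rule is the one already applied to the Autoimmune Cohort, so the subset exists. The cost is a few lines of protocol and analysis-plan text, some extra analysis, and wider intervals because recent joiners drop out of the restricted analysis. Look-back reduces mislabelling without removing it: doses never billed to the plan, and doses under other coverage more than 12 months earlier, can still go unseen. The 12-month limit on the series binds Completers only, so an Initiator's doses may be further apart.
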